#### 14.0 Sponsor Pulse Oximeter Study Data

14.1 Data from test pulse oximeters for comparison to blood values can be obtained in several ways. In every case, the goal is to obtain a reading from the oximeter that corresponds to the associated blood sample or a reference oximeter. Because of circulation delays and instrument averaging time, attempts will be made to create steady state conditions at each level of oxygenation. Therefore, a means should be provided to record the instrument reading at each blood sample. This instrument reading may be obtained with several different approaches. Some instruments have no digital or analog output and the instrument reading may be recorded manually or recorded by a video of the instrument display. Other instruments may have an analog output. The laboratory can record analog data by use of LabView. Digital recording of output can also be

DF-CDS-109-11
Rev. L
Sustainability Document Template

Document No:	CRD10351
Revision:	Α
Page:	8 of 11

obtained via LabView but this requires information from the sponsor concerning the structure of the digital signal.

14.2 If a manufacturer prefers to collect and analyze the data, the continuous digital signal of each oximeter should be read, for comparison with the blood sample, 9 seconds before the record shows a sudden fall or rise in oxygen saturation, not at the time of blood sampling. This procedure accounts for the delays of finger circulation and uses the estimated delay from the lung to the sample site. There is no useful correlation between the actual time of blood sampling and the oximeter recording because of the variability of tissue blood flow lag. As mentioned, steady-state hypoxia avoids the concern that oximeter reading is not aligned with a blood sample reading.

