#### **Procedure**

#### 7.0 **Summary**

Study Design:	T	
Study Type:	Interventional Non-significant Risk Lab Test	
Enrollment:	A typical study wi	ll include at least 10 subjects (up to 24 if needed to reach the 200
	necessary data po	oints to meet the ISO 80601-2-61:2019).
Allocation:	Non-randomized	
Intervention Model:	Parallel Assignmen	nt
Intervention Model Description:	Subjects will reclin	ne for the study. Reference sensors will be placed on each subject
	to evaluate the Sp	OO 2 accuracy and performance. Shield material may be used
	between any adjacent finger sensors to prevent optical crosstalk. A machine will	
	be used to induce motions of up to 20 mm during testing at a sine rate of 2Hz, 3Hz,	
	and 4Hz. A third motion moves the arm a random distance of up to 30mm at a	
	random speed up to 5Hz. Simultaneous data collection will be set up for devices	
	under test. The data from the test devices will be collected by the sponsor or	
	trained UCSF staff. Data will be collected for 1 second intervals data analysis. The	
	SpO 2 accuracy of the test devices will be evaluated over the oxygen saturation	
	range between 70-100%.	
Masking:	None (Open Label)	
Primary Purpose:	Device Validation	
Study Start Date:	May 27-28, 2023	
Arms and Interventions:		
Experimental: Masimo RD SET SpO2	2 Adhesive	Device: Stryker Sustainability Solutions Reprocessed Masimo
Sensors, Adult (4000 Adt), Adult & Neonate (4003		RD SET Pulse Oximetry Sensors

Neo)

Reference sensors from the reprocessed oximeter device will be placed on each subject to evaluate the SpO2 accuracy and performance.

An oximeter is a device used to transmit radiation at a known wavelength(s) through blood and to measure the blood oxygen saturation based on the amount of reflected or scattered radiation. Pulse oximetry monitoring is considered a standard physiological measurement and is used by clinicians in everyday situations to estimate arterial oxygen saturation. Because an arterial sample of blood is not required to make the measurement, the pulse oximeter can provide non-invasive real time information.

DF-CDS-109-11	UNCONTROLLED WHEN PRINTED
Rev. L	STRYKER CONFIDENTIAL - This document contains confidential and proprietary
Sustainability Document Template	information that is the property of Stryker Corporation. Neither this document nor the information herein may be reproduced, used or disclosed to any third party without the prior written consent of Stryker Corporation.

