#### 13.0 Procedure

- 13.1 If the principal investigator deems it necessary, the subject may be asked to run hot water over hands and arms for 5 minutes to improve perfusion. After injection of a local anesthetic, a 22-gauge catheter is inserted in one radial artery. Pulse oximeters are attached to fingers with adequate spacing between fingers or shielding to minimize device cross-talk. Subjects are in a comfortable semi-recumbent position. Subjects then breathe air mixtures containing reduced amounts of oxygen to produce the desired level of hypoxemia. Stable, safe and controlled hypoxia is adjusted manually by an anesthesiologist that permits the inspired gas mixture to be adjusted to achieve a level of lung alveolar gas that will achieve the desired degree of saturation.
- 13.2 Typically, saturation levels involve one period with air breathing and then at one of three or six levels, e.g. 94%, 90%, 85%, 80%, 75% and 70% or 95%, 85% and 75% saturation. Each level of saturation is held for 30-60 seconds or 60-90 seconds respectively. At appropriate intervals and when oxygen levels are stable, arterial blood samples are obtained from the radial arterial catheter. The operator then changes the inspired oxygen concentration to attain the next desired stead-state level of hypoxia. This study should utilize a three level structure (95%, 85% and 75%). A "run" consists of several stable steady-state hypoxia levels and together takes approximately 20 minutes. Each run is terminated by a breath of 100% O2 followed by room air. Two runs together enable obtaining a total of 20-25 blood samples, 4 samples at each plateau. Saturation of each arterial blood sample is determined by direct oximetry in a Radiometer ABL-90 multi-wavelength oximeter. The precise target levels of saturation can be adjusted to suit the sponsor, but typical testing is done to satisfy ISO and FDA standards for testing, which is 70% to 100%.
- **13.3** The study takes under 2 hours of each subject's time. Analysis of the data requires several days. Manufacturer's representatives (Stryker) will be present for these tests, and to mount the probes.

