#### 16.0 Data Analysis

- **16.1** In all cases, the blood analysis data are provided, including the SaO2, MetHb, COHb and Hgb concentration.
- **16.2** The data analysis report will consist of the following:
  - **16.2.1** A Table of the oximeter readings versus corresponding blood SaO2 values.
  - **16.2.2** Graphic plots of the bias between the oximeter reading and the SaO2 measured by the hemoximeter (on the blood sample, i.e Modified Bland-Altman plots for each instrument or instrument probe combination).
  - **16.2.3** Regression equations for the bias of each instrument.
  - **16.2.4** Tables of the mean error or bias, its standard deviation, standard error, 95% confidence interval, maximum and minimum and root mean square error, all computed both overall and by several sub-ranges of desaturation.
  - **16.2.5** A table of the demographics of the subject population is provided.

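### The plan does not require SpO2 readings and exclusions to be fixed by one rule, or by a reader without access to SaO2, before the CO-oximeter results are provided

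*Combined protocol and SAP*

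**What the plan says.** - **Who handles the data.** The study is open label (Section 7.0). On collection, the same section says: "The data from the test devices will be collected by the sponsor or" trained site staff. Section 14.2 adds a conditional option: "If a manufacturer prefers to collect and analyze the data, the continuous digital signal of each oximeter should be read". The plan does not say which route this study uses.
- **Where the reading is taken.** Section 14.2 places it "9 seconds before the record shows a sudden fall or rise in oxygen saturation, not at the time of blood sampling". Section 14.1 instead asks for a means of recording the instrument reading at each blood sample, and lists manual, video, analog and digital capture without choosing one. Section 7.0 plans device data at 1-second intervals.
- **Reference values.** Section 16.1: "In all cases, the blood analysis data are provided, including the SaO2, MetHb, COHb and Hgb concentration". No time, recipient or order of release is given.
- **Lost readings.** Section 15.1 accepts that some readings may be lost to interference. It gives no rule for declaring this.
- **Verdict.** Sections 7.0 and 25.1.1 compare the Arms point estimate with 3%, on at least 200 data points. Section 7.0 applies the limit to each sensor style.

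**The concern.** The only endpoint is the difference between an SpO2 reading and its paired SaO2 value. If the person who picks the reading, or decides that it is unusable, can see the SaO2 value, any choice made with that knowledge tends to shrink the difference. The error then runs in one direction, towards a pass. Agreeing on one pairing rule would narrow the room for choice, but a rule that still relies on judgement leaves some of it. The order in which the two sets of values become known therefore needs its own statement. At stake is a pass/fail decision at a fixed limit, in a study meant to support a regulatory submission (Section 1.2).

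**Working it through.** **1. The plan's own count.** The minimum is 200 pairs and 10 subjects (15.1). Section 13.2 gives 20–25 samples per subject over two runs, 4 per plateau, at three levels.
- 10 × 20 = 200, which reproduces the minimum; 10 × 25 = 250.
- 4 samples × 3 levels × 2 runs = 24 per subject, inside 20–25. Ten subjects give 240 pairs per style, assuming each subject wears one sensor of each style.
- 240 − 200 = 40 pairs (16.7%) could be lost with the minimum still met.

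The plan has no alpha, power, SD or expected Arms to reproduce. The values below are assumptions.

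**2. Does Section 14.2 fix the reading?** Three plateaus in each of two runs end in 3 × 2 = 6 changes of saturation, so the rule yields about 6 reading points for 24 samples. The other samples have no uniquely determined reading. The landmark must be located in a trace recorded during induced motion. Section 14.1 points to the time of the draw, which Section 14.2 rejects. The rule limits choice but does not remove it.

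**3. Favourable exclusion.** For zero-bias, roughly normal differences, dropping the largest fraction f multiplies Arms by √(1 − 2cφ(c)/(1 − f)), with c = z(1 − f/2). For f = 5%: c = 1.960, φ(c) = 0.0584, ratio = √(1 − 0.229/0.95) = 0.871, and 3.0/0.871 = 3.44.

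| Worst pairs dropped | Ratio | True Arms that reads as 3.0% |
|---|---|---|
| 2% | 0.935 | 3.21% |
| 5% | 0.871 | 3.44% |
| 10% | 0.789 | 3.80% |
| 16.7% | 0.701 | 4.28% |

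In simulation (10 subjects × 24 pairs, between-subject SD 1 point), a sensor with true Arms 3.2% passes about 11% of the time with no selection. It passes 53%, 92% and 99.9% of the time if the worst 2%, 5% and 10% are dropped. These are limiting cases, because they assume that exactly the worst pairs go.

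**4. Favourable placement.** Assumptions: 10 × 24 pairs, between-subject SD 1 point, SpO2 in whole percent, serially correlated fast error (correlation time 10 or 30 s), pass if Arms ≤ 3.0. At true Arms 3.3% the non-subject SD is √(3.3² − 1²) = 3.14 points. One reading in four is moved to the second with the smallest difference within ±2 or ±5 s.

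| Error structure | Fixed reading | 1 in 4 moved |
|---|---|---|
| All non-subject error varies within seconds | about 3% pass | 19–70% pass |
| Fast part SD 0.5–1 point, rest constant per plateau | about 13–18% pass | 19–32% pass |

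In the first row, ±2 s gives the low end and ±5 s with a 10 s correlation time the high end. The unselected pass rate is higher in the second row because the error then rests largely on 10 × 6 = 60 plateau values and not on 240 separate ones, so Arms varies more between trials.

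If every reading is moved, at true Arms 3.5%, 94–100% pass under the first structure. Under the second, 19–69% pass with a fast SD of 1 point and 12–32% with 0.5.

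**The case against.** A reader might infer that the sponsor reads SpO2 with the SaO2 results in hand. The documents do not say so. Section 16.1 states that blood data are provided, not when or to whom. Sponsor reading is one option beside trained site staff, and Section 14.2 introduces it conditionally.

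Other tempting inferences also fail:
- Open label is not itself the fault. Both measurements are instrument readings.
- The sponsor's presence to mount the probes (13.3) gives no means of choosing readings.
- The phrase "the instrument reading may be recorded manually" in Section 14.1 concerns instruments without digital or analog output, whereas Section 7.0 plans a 1-second record. A value copied live at the draw would also normally precede that sample's blood result.
- Nothing suggests that stability before a draw is judged on the test display. Section 20.0 has reference oximeters and end-tidal analysis in use, though for safety.

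The 9-second offset is a real constraint. Section 14.2 also relies on steady state, which would leave less to gain from moving a reading by a few seconds, and Section 16.2.1 requires a table of readings against SaO2. These points reduce the likely size. They do not close the gap: much of the discretion comes from the unresolved pairing rule, the table shows the chosen reading but not the alternatives, and no section masks the reader or locks the values first.

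**Conclusion.** The point holds as an unblocked possibility, not as a stated practice. The plan neither fixes SpO2 readings and exclusions by one complete rule nor keeps SaO2 from whoever extracts them, and any resulting bias would favour a pass.

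Its size depends on how much of the error varies within seconds, which the documents do not give. For a sensor just above the limit (true Arms 3.3%), the gain in pass rate runs from a few points to more than 60. The one-in-four fraction, the search windows and the error SDs are all assumed, so the figures show how sensitive the verdict is and are not an estimate of expected bias. Nor are they evidence that selection occurred. Confidence is medium.

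**What to change.** In Section 14:

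1. Reconcile 14.1 and 14.2 into one pairing algorithm that gives a reading for every draw from the time-stamped 1-second record, or assign extraction to a named role without access to SaO2.
2. State the rule for excluding a reading, applied without SaO2.
3. Lock the SpO2 values and exclusions for all draws in a dated file before CO-oximeter results are released to whoever extracts them, and state this order in 16.1.
4. Merge the two files by draw number, and report Arms with and without the excluded pairs.

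Subjects and staff can otherwise stay unmasked. The cost is protocol wording and the order of two data transfers, since the 1-second record is already planned. The small downside is that the sponsor sees accuracy results only after the SpO2 file is locked.

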#### 15.0 Statistics

- **15.1** The number of subjects and the number of comparisons (paired pulse oximeter readings and arterial saturation values) is determined by current FDA guidance requirements. This is a minimum of 200 data points and 10 subjects. In the course of this type of study, some subjects may drop out, some readings can be lost due to interference and occasionally some do not consent.
- 15.2 The following demographic data will be collected on the subjects:
  - 15.2.1 Gender (male, female, other)
  - 15.2.2 Age
  - **15.2.3** Skin pigmentation (dark, medium, light) preferably 1-6 using the Fitzpatrick scale
  - **15.2.4** Height (cm)
  - **15.2.5** Weight (kg)
  - 15.2.6 Wrist circumference (cm)
  - 15.2.7 Dominant hand (left or right)

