#### 2.0 Scope

2.1	This procedure applies to the following Stryker Sustainability Solutions location(s):

	⊠ Tempe	□ Phoenix	□ Lakeland		☐ Chandler
--	---------	-----------	------------	--	------------

2.2 This study has been designed to include the subject devices listed in Table 1.

Study Device:			
OM	SKU	Minimum Quantity	Cycle Count
Masimo	4000 Adt (Adult)	10	4x
Masimo	4003 Neo (Adult & Neonate)	10	4x

Table 1: Subject devices

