#### 10.0 Sample Size Designation

- 10.1 A typical study will include at least 10 subjects (up to 24 if needed to reach the 200 necessary data points to meet the ISO 80601-2-61:2019). Per FDA guidance, at least 2 or 15% of the subjects will have dark skin pigmentation. Skin pigmentation will be assessed using the Fitzpatrick scale by UCSF study personnel.
- 10.2 Each study subject will have two reprocessed sensors attached to their fingers. Two Reprocessed Masimo RD SET sensors should be placed on one side of the subject; however, sensors may be placed opposite sides. Digits selected should be two of the three middle fingers on each hand avoiding the thumb or pinky fingers as test sites.

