#### 23.0 Monitoring Arrangements

- **23.1** A representative from the sponsor and study monitor will provide all monitoring. The Monitor shall be responsible for maintaining a record of the findings, conclusions, and actions taken for the results of monitoring the study ensuring that:
- 23.2 The monitoring requirements for an NSR device study is identified in 21 CFR 812.2(b) Abbreviated requirements. For monitoring an NSR device investigation, the requirement is to comply with 21 CFR 812.46 with respect to monitoring investigations: (a) Securing Compliance, (b) Unanticipated adverse device effects, (c) Resumption of terminated studies
  - Compliance to the signed agreement between the Investigator and sponsor
  - The study follows the protocol and any amendments that apply
  - Compliance to any conditions of the approval imposed by the IRB or FDA
- **23.3** Sponsor will assess any new hazards/harms identified during a clinical investigation (i.e., pre- or post-market study) as part of the risk management process per DPCDS-013, Risk Management and the complaint handling process per DP-MCF-001, Division Complaint Handling Process, as applicable.

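### Does the remark in 15.1 that readings may be lost to interference leave the data behind the 3% motion ARMS open to selection?

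*Combined protocol and SAP*

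**What the plan says.** Section 15.1 sets the minimum at 200 paired points and 10 subjects, then adds that "some subjects may drop out, some readings can be lost due to interference and occasionally some do not consent". It does not define a lost reading, name the interference, or give an expected rate.

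The other provisions that bear on the point are these:

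- **Crosstalk.** This is the one form of interference named elsewhere. Section 7.0 allows shield material "between any adjacent finger sensors to prevent optical crosstalk", and 13.1 asks for "adequate spacing between fingers or shielding to minimize device cross-talk". Section 10.2 says "Two Reprocessed Masimo RD SET sensors should be placed on one side of the subject", though it also permits opposite sides.
- **Recording and pairing.** Section 14.1 aims in every case for an oximeter reading that corresponds to the blood sample and asks for a means of recording one at each sample. Section 14.2 gives a different timing rule under a condition: "If a manufacturer prefers to collect and analyze the data".
- **Outcome.** The ARMS formula under Primary Outcome Measures sums squared differences over all n pairs. The 3% limit applies to each sensor style.
- **Reporting.** Section 16.1 states "In all cases, the blood analysis data are provided". Section 16.2 adds a table of readings against SaO2, bias plots, and minimum and maximum errors.
- **Acceptance.** Section 25.1.1 requires at least 200 points and an ARMS of 3% over 70-100%. It sets no condition on exclusions.
- **Oversight.** The study is open label, the sponsor may collect the device data, and under 23.1 "A representative from the sponsor and study monitor will provide all monitoring".

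**The concern.** The study exists to measure error under motion. If a displayed value could be set aside as interference, the readings most likely to be set aside would be those furthest from SaO2, which are the failures the study is meant to count. Nothing in the text requires that decision to be made without sight of the blood result: there is no masking, the sponsor may handle the device data, and the blood values are always supplied.

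The pass rule is a point estimate of a squared-error measure, so a few large errors can decide it. The 200-point minimum is no safeguard when more than 200 pairs are collected. The same recording might fail with every displayed pair included and pass with a few removed. Loss unrelated to the size of the error would not bias ARMS; the worry is confined to displayed values that are later excluded.

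**Working it through.** **Number of pairs.** Section 13.2 gives three levels, 4 samples per plateau and two runs: 3 x 4 x 2 = 24 draws, inside its stated 20-25. Section 2.2 says "This study has been designed to include the subject devices listed in Table 1", and that table lists at least 10 sensors of each style, which fits one of each style on 10 subjects. Per style:

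| Draws per subject | Pairs, 10 subjects | Spare above 200 |
|---|---|---|
| 20 | 200 | 0 |
| 24 | 240 | 40 (40/240 = 16.7%) |
| 25 | 250 | 50 (50/250 = 20%) |

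The first row reproduces the plan's minimum, 10 x 20 = 200. Requiring 200 points per style is an assumption; the documents state the per-style condition only for ARMS.

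**Worst case: every excluded reading is a large error.** Let the kept readings have ARMS K and let n excluded readings each have error L. All 240 together fail when

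((240 - n) x K² + n x L²) / 240 > 9.

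The smallest n that satisfies this is:

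| Kept ARMS K | L = 6 | L = 8 | L = 10 |
|---|---|---|---|
| 2.8% | 10 | 5 | 4 |
| 2.5% | 23 | 12 | 8 |
| 2.0% | 38 | 21 | 13 |

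Example: K = 2.8, L = 10, n = 4 gives (236 x 7.84 + 4 x 100)/240 = 9.376, so ARMS is 3.06%. With n = 3 it is 2.999%. Between 202 and 236 pairs remain, so the 200-point minimum never stops it. This shows what is possible if exclusion is perfectly targeted.

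**Partial selection.** Take normal errors with mean 0 and SD S, and suppose half of the readings with error beyond 6 points are excluded. With z = 6/S, p = 2(1 - Φ(z)) and t = 2(zφ(z) + 1 - Φ(z)), the kept ARMS is

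S x √[(1 - 0.5t)/(1 - 0.5p)].

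- S = 3.20: z = 1.875, p = 0.0608, t = 0.3187; kept ARMS 2.98%, with 0.5 x 0.0608 x 240 = 7.3 readings removed. Pass.
- S = 3.23: kept ARMS 3.00%, the turning point.
- S = 3.30: kept ARMS 3.05%. Fail.
- S = 3.50: kept ARMS 3.20%. Fail.

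Under this milder selection the verdict changes only for a starting ARMS between 3.0% and about 3.23%.

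**Unrelated loss.** Dropping 12 of 240 at random from a 3.3% set leaves the mean ARMS at 3.3% (20,000 simulations).

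**What the text permits.** None of the arithmetic applies unless a displayed value may be removed. Section 15.1 lists lost readings with drop-outs and non-consent, directly after the minimum counts. In that setting it explains why the minimum might not be reached from the first 10 subjects, and 10.1 answers it by allowing up to 24. No section authorises removal. Section 14.1 and the ARMS formula point the other way: record a reading at each sample and sum over all pairs.

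**The case for a change.** The best case for a change is that silence is not a safeguard. The protocol neither defines a lost reading nor says who decides, and a value distorted by crosstalk might look like one distorted by motion. Unpaired draws could be inferred by comparing the blood data with the paired table, but the reasons for loss could not. A sentence keeping every displayed value would cost little beyond a revision and IRB review under 22.3.

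Part of this stands: the word is undefined, and no exclusion rule for displayed values appears. Whether the cited ISO annex or FDA guidance contains one cannot be checked from the documents.

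The rest is weaker. Section 15.1 does not equate interference with crosstalk. Sections 7.0 and 13.1 mention crosstalk only as something to prevent or reduce, and no section says it leaves a wrong value on display that cannot be told from motion error. Manufacturer analysis in 14.2 is conditional, and 23.1 concerns monitoring of compliance, not choice of data.

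A rule that a reading is lost only when no valid value is shown, or when the draw, SaO2 result or recording failed, would also need the 70-100% SaO2 limit. Without it, a pair at 69% would enter the primary ARMS, against 25.1.1. It would also have to say how the 1-second values are combined. A table of lost and attempted pairs would help readers but would not alter the estimate. The tension in timing between 14.1 and 14.2 is a separate matter.

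**Conclusion.** The concern does not call for a change. Followed as written, the plan pairs a reading with each blood sample and computes ARMS over all the pairs for each style, which is sound. The gap is a missing definition that analysts would fill sensibly by treating a lost reading as one not obtained.

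The possible effect is real but conditional. With 240 pairs per style, fully targeted removal of 4 to 38 readings could reverse a fail, depending on the assumed errors. Removing only half of the errors beyond 6 points reverses it just for a starting ARMS of 3.0% to about 3.23%. At 20 draws per subject and 10 subjects there are no spare pairs at all. These figures rest on assumed error sizes, normal errors in the partial case, and 200 points required per style. They show what selective exclusion could do, and the documents do not show that any is planned.
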